8. RESEARCH QUESTION AND OBJECTIVES

DAA-PASS is designed to investigate the question: does DAA therapy for chronic HCV infection increase the risk of early HCC recurrence among a well-characterized group of patients who have received successful HCC treatment interventions, relative to no DAA therapy?

Primary Objective	Primary Endpoint
Estimate the risk of early HCC recurrence (within the follow up period after the first HCC-free image) associated with DAA therapy exposure relative to no DAA therapy exposure during routine clinical care of HCV-infected patients with successfully treated HCC, in the prospective DAA-PASS cohort.	Time to recurrence of HCC (from radiological confirmation of the absence of detectable disease following HCC treatment intervention) associated with DAA therapy exposure relative to no DAA therapy exposure in the prospective DAA-PASS cohort.
Secondary Objectives	Secondary Endpoint
A. Compare the adjusted incidence of early HCC recurrence (within the follow up period after the first HCC-free image) associated with DAA therapy exposure relative to no DAA therapy exposure during routine clinical care of HCV-infected patients with successfully treated HCC, in the prospective DAA-PASS cohort.	A. Number of events (early HCC recurrence) associated with DAA therapy exposure relative to no DAA therapy exposure, in the prospective DAA-PASS cohort.
B. Estimate the risk of early HCC recurrence (within the follow up period after the first HCC-free image) associated with DAA therapy exposure relative to no DAA therapy exposure including a historical cohort of HCV patients not exposed to DAA with initial HCC diagnosis and subsequent successful treatment of HCC.	B. Time to recurrence of HCC (from radiological confirmation of the absence of detectable disease following HCC treatment intervention) associated with DAA therapy exposure from the prospective DAA-PASS cohort relative to no DAA therapy exposure including the historical cohort.
C. Compare the adjusted incidence of early HCC recurrence (within the follow up period after the first HCC-free image) associated with DAA therapy exposure relative to no DAA therapy exposure including a historical cohort of HCV patients not exposed to DAA with initial HCC diagnosis and subsequent successful treatment of HCC.	C. Number of events (early HCC recurrence) associated with DAA therapy exposure from the prospective DAA-PASS cohort relative to no DAA therapy exposure including the historical cohort.

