9.7.8. Evaluation of Incidence of HCC Recurrence (Secondary Objectives A and C)

Secondary Objectives A and C are to evaluate the adjusted incidence of recurrence of HCC using the endpoint of the number of events.

An analysis approach based on inverse-probability of censoring weighted averages (IPCW) as outlined in Satten and Datta¹⁶ will be used to obtain an adjusted estimate of the cumulative risk and expected total events for the prospective cohort under the assumption that none of the participants had received DAA. For this analysis, a proportional hazards model of the time-to-censoring event of the non-DAA HCC exposure caused by the start of DAA exposure using the primary analysis covariates will be performed. The model parameters will give individual participants IPC weights in order get an adjusted estimate of the cumulative risk and total events had participants not gotten DAA exposure.

This estimate of risk will be compared to the actual observed risk in the cohort (estimated by the complement of the Kaplan-Meier estimator) to assess the impact of DAA use on HCC recurrence in the prospective cohort. The results will be presented at follow-up time points of 3, 6, 9, 12, 18, and 24 months.

In order to obtain CIs for the estimated risk difference and differences in number of HCC recurrence events at each of the time points, bootstrapping will be used to resample participants from the entire prospective population.

The estimated and actual cumulative event counts will be displayed at the indicated time points. Survival and cumulative event curves will be displayed in figures. Information on significance of the modeling parameters used in the IPCW model will be provided.

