The analysis for Secondary Objective B will mirror that of the Primary Objective by integrating data from the prospective and historical cohorts. Participants in the prospective cohort with DAA exposure will contribute person-time at risk to both the DAA-exposed condition and the unexposed condition (i.e., the time prior to DAA exposure). Participants in the prospective cohort who never receive DAA therapy during follow-up and all participants in the historical cohort will contribute person-time at risk to the unexposed condition only.

For Secondary Objective C, the assessment of adjusted incidence of HCC recurrence analysis based on the IPCW approach (described in Section 9.7.8) will be performed by integrating data from the prospective and historical cohorts. Similar to the analysis for the Primary Objective, this will be used to provide an estimate of the cumulative incidence rate and number of events in participants receiving DAA therapy when compared to the estimated rates of those participants if they had not received DAA therapy.

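### Secondary Objectives A and C ask for DAA-exposed versus unexposed incidence, but section 9.7.8 compares nobody treated with the whole cohort as observed, and the protocol gives three different contrasts for C

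*Protocol*

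**What the plan says.** Section 8 opens Secondary Objective A with "Compare the adjusted incidence of early HCC recurrence (within the follow up period after the first HCC-free image) associated with DAA therapy exposure relative to"; the other side of the comparison is the absence of DAA therapy. Objective C asks the same with the historical cohort included.

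Section 9.7.8 gives the method for both. Inverse-probability-of-censoring weights, from a model for the time to DAA start, yield the cumulative risk and event total "under the assumption that none of the participants had received DAA". Then: "This estimate of risk will be compared to the actual observed risk in the cohort", the latter being one minus Kaplan-Meier. The stated purpose is "to assess the impact of DAA use on HCC recurrence in the prospective cohort". The objectives are evaluated "using the endpoint of the number of events", and intervals are promised for both the risk difference and the event-count difference. For those intervals, "bootstrapping will be used to resample participants from the entire prospective population".

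Section 9.7.9 opens by describing the incidence comparison as one between exposed and non-exposed patients. Its last paragraph says that the 9.7.8 approach "will be performed by integrating data from the prospective and historical cohorts", and describes the result as a cumulative rate together with the "number of events in participants receiving DAA therapy when compared to the estimated rates of those participants if they had not received DAA therapy".

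**The concern.** The two sides of the 9.7.8 comparison are not exposed and unexposed. One side is a cohort in which nobody is treated. The other is the cohort as it was, including everyone who has not yet started DAA or never will. Early in follow-up few have started, so the two curves must lie close together whatever DAA does. Yet early recurrence prompted the study: section 7.2 cites a report with a median of 3.5 months from DAA start to recurrence. A small early difference in A could be read as reassurance when it mainly reflects low uptake at that time.

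For C, a programmer cannot follow 9.7.8, the opening of 9.7.9 and its last paragraph together. The choice among them fixes both the size of the reported risk difference and whose sampling error the interval covers.

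**Working it through.** **Inputs.** DAA uptake among recurrence-free participants: 42% by month 6, 86% by month 12, 90% by month 24 (section 9.5.1). Hazard ratio of concern: 2.0 (9.5.1). Annual recurrence r: 15%, 25%, 35% (9.7.9). Cohort sizes for C: 50 prospective and about 400 historical (9.7.9). Prospective range: 40 to 70 (4.8).

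The protocol states no expected size or precision for the A or C contrast, so there is no figure to reproduce. Its event counts for 600 participants (122 and 195) include censoring at an unstated rate. Without censoring they would be 600 × (1 − 0.85²) = 166.5 and 600 × (1 − 0.75²) = 262.5. The model below has no censoring.

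**Objective A.** Let λ = −ln(1 − r)/12 per month, and let G(t) be the uptake, linear between the stated points, with density g.

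- Nobody treated: R0(t) = 1 − exp(−λt)
- DAA from day 0: R1(t) = 1 − exp(−2λt)
- Observed mixture: Robs(t) = 1 − {[1 − G(t)]·exp(−λt) + ∫₀ᵗ g(s)·exp[−λs − 2λ(t − s)] ds}

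Month 6, r = 25%: λ = 0.02397. The not-yet-treated term is 0.58 × 0.8660 = 0.5023. The treated term is 0.07 × 0.75 × (1.1547 − 1)/0.02397 = 0.3388. So Robs = 15.9%, R0 = 13.4%, R1 = 25.0%. The planned contrast is 2.5 points and the full one 11.6, a share of 21%.

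Risk differences in percentage points, full (R1 − R0) / planned A (Robs − R0):

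| Month | r = 15% | r = 25% | r = 35% | Share shown by A |
|---|---|---|---|---|
| 3 | 3.8 / 0.4 | 6.5 / 0.7 | 9.2 / 1.0 | 11% |
| 6 | 7.2 / 1.5 | 11.6 / 2.5 | 15.6 / 3.4 | 21-22% |
| 12 | 12.8 / 5.6 | 18.8 / 8.4 | 22.8 / 10.4 | 44-46% |
| 24 | 20.0 / 13.6 | 24.6 / 17.1 | 24.4 / 17.4 | 68-71% |

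Over hazard ratios of 1.5 to 3 the shares are about 11%, 21-23%, 43-49% and 66-77%.

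**Objective C: the three statements.**

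| Place | Contrast |
|---|---|
| 9.7.8 | Nobody treated versus observed risk in the cohort; impact and bootstrap tied to the prospective cohort |
| 9.7.9, opening | DAA-exposed versus non-exposed patients |
| 9.7.9, last paragraph | DAA recipients versus the same recipients untreated, by the 9.7.8 approach on integrated data |

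**If the 9.7.8 steps were run on the pooled data.** The historical patients are unexposed by design: 400/450 = 89% (91% with 40 prospective, 85% with 70). With equal baseline risk, the pooled risk difference is A's times 50/450, one ninth. At r = 25% that is 0.3 points at month 6 (2.5/9) and 1.9 at month 24 (17.1/9). The event-count difference does not shrink: 50 × 17.1% and 450 × 1.9% are both about 8.5 events at month 24.

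**Data behind the no-DAA curve in A.** Unexposed at risk = N·[1 − G(t)]·(1 − r)^(t/12), without censoring.

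| | Lowest (N = 40, r = 35%) | Highest (N = 70, r = 15%) |
|---|---|---|
| Month 12 | 40 × 0.14 × 0.65 = 3.6 | 70 × 0.14 × 0.85 = 8.3 |
| Month 24 | 40 × 0.10 × 0.4225 = 1.7 | 70 × 0.10 × 0.7225 = 5.1 |

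So about 4-8 remain at month 12 and 2-5 at month 24.

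**The case against.** Observed course versus nobody treated is a recognised population-impact contrast, and 9.7.8 states that purpose. The benchmark above, everyone on DAA from day 0, is not in the protocol, and the early gap simply reflects that 42% have started by month 6. The exposed-versus-unexposed hazard ratio is already the primary analysis. All of this is fair, and it means the contrast in A may stay. It does not make the contrast answer the objective as worded, and a reader of the results would not know how far the two differ.

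A reader might go further and infer that the DAA effect nearly vanishes in C because about 89% of patients are unexposed. The documents do not support that as a certainty. Section 9.7.8 ties its contrast to the prospective cohort, and the end of 9.7.9 describes it in DAA recipients; on either reading the historical patients do not dilute it. The near-vanishing needs the observed risk to be that of the pooled data, and even then it touches only the risk difference, not the event count that is the named endpoint. Nor can the small pooled difference be judged against the standard error of a single curve, because both curves share the same 400 patients and much of that error cancels.

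Section 9.7 makes the analyses contingent on final numbers and leaves detail to the SAP. A SAP can add detail, but it cannot satisfy three incompatible contrasts.

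**Conclusion.** The point holds in two parts. In A, the stated method does not estimate the stated objective; under the section 9.5.1 uptake it shows roughly a tenth of the full risk difference at month 3, a fifth at month 6, under half at month 12 and about 70% at month 24. These shares assume constant hazards, linear uptake, no censoring and no confounding, and change little across the protocol's recurrence rates. In C, the finding is a contradiction between 9.7.8 and two places in 9.7.9 about whose risk is compared, together with a bootstrap that resamples prospective participants only. Applied as written to pooled data, that bootstrap would leave historical sampling error out of the interval. The one-ninth shrinkage in C is conditional on a literal pooled reading and on equal baseline risk. The primary hazard ratio is not affected.

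**What to change.** - State one estimand for A and C that matches section 8, and align 9.7.8 with 9.7.9. Two candidates are standardised risk under DAA versus no DAA for the prospective participants, or the effect in DAA recipients as the end of 9.7.9 describes.
- Keep the observed-versus-none comparison if wanted, labelled as population impact.
- In C, use historical patients only to inform the no-DAA curve. Fit the DAA-start model in the prospective cohort, since historical patients were selected for not receiving DAA. Bootstrap within each cohort.
- Print the number of unexposed participants at risk beside each time point. A fixed minimum for stopping the curve is not needed: a cut-off of 10, for example, would already remove month 12.

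The cost is protocol and SAP wording plus programming, with no new data. The drawback is that the DAA curve becomes more dependent on a model.

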9.7.9. Secondary Analyses Using the Historical Cohort

The analyses to address Secondary Objectives B and C will (1) estimate the risk of early HCC recurrence associated with DAA therapy exposure relative to no DAA therapy exposure during routine clinical care of HCV-infected patients with previous successfully treated HCC, and (2) estimate the incidence of early HCC recurrence among DAA exposed vs. DAA non-exposed patients, by integrating data from the prospective DAA-PASS cohort with data from a historical cohort of HCV patients with no DAA exposure, to permit adjustment for covariates that may differ between patients in the prospective and historical cohorts.

The ITA.LI.CA study cohort has been identified as a source of historical data for this analysis. The ITA.LI.CA database collects data on all consecutive consenting adult patients with HCC who were diagnosed after 2007 (when the database began to capture follow-up clinical and imaging data) and who were managed at ITA.LI.CA participating centers in Italy. Patients were diagnosed with HCC and followed up in each center according to diagnostic and clinical management guidelines at that time. Approximately 40% of patients in ITA.LI.CA are BCLC Stage A at initial HCC diagnosis, and the median follow-up of patients is 24 months. Patient-level data were abstracted from medical records at the time of initial HCC diagnosis and treatment; subsequent data abstractions were performed at the time of any HCC recurrence event. The last verified database update was in December 2016.

The ITA.LI.CA database will be used to assemble data for a historical cohort of HCV-infected patients who were successfully treated for BCLC Stage A HCC with curative therapy, and not treated with DAAs for their HCV infection after HCC diagnosis. Per the ITA.LI.CA investigators, practice among the ITA.LI.CA participating hospitals was such that patients who had HCV (either treatment-naïve or previously treated with IFN-based therapy) were not treated with IFN after successful HCC treatment. A small number of recently-enrolled patients were treated with DAAs; these patients will be excluded from the historical cohort. Therefore, the patients for the historical cohort will include patients who have active HCV infection who were not treated for HCV (IFN-based or DAA-based regimens) during the follow-up period. Prior HCV treatment with IFN-based non-DAA regimens prior to HCC will be allowed. After considering the aforementioned inclusion/exclusion criteria for the prospective DAA-PASS, an initial examination of the ITA.LI.CA database indicates that there will be approximately 400 eligible patients for inclusion in the historical cohort.

The historical cohort will include similar data extracted from the ITA.LI.CA database (where available) as that collected in the prospective DAA-PASS cohort (see Section 9.3). The ITA.LI.CA database includes patient-level data on demographics (sex, age, birth province),

laboratory values, comorbid liver conditions (including but not limited to HCV status), medical history events, concomitant medication use (including hepatotoxic medications), alcohol use, staging of liver disease, HCC diagnosis and tumor characteristics, HCC treatment intervention(s), and prior interferon-based HCV treatment.

Based on a convenience sample size of 50 participants in the prospective cohort and the inclusion of approximately 400 historical cohort participants the expected 95% CI of the HR (assumed to be equal to 1.0) based on a 15% annual recurrence rate is 0.51 to 2.13, and based on a 25% annual recurrence rate is 0.57 to 1.82, and based on a 35% annual recurrence rate is 0.62 to 1.69.

Descriptive summaries for the historical cohort will be provided in similar formats provided for the prospective cohort. Statistical tests will be used to test the null hypothesis that the historical and prospective cohorts are homogeneous with respect to available demographics and baseline disease characteristics.

The analysis for Secondary Objective B will mirror that of the Primary Objective by integrating data from the prospective and historical cohorts. Participants in the prospective cohort with DAA exposure will contribute person-time at risk to both the DAA-exposed condition and the unexposed condition (i.e., the time prior to DAA exposure). Participants in the prospective cohort who never receive DAA therapy during follow-up and all participants in the historical cohort will contribute person-time at risk to the unexposed condition only.

For Secondary Objective C, the assessment of adjusted incidence of HCC recurrence analysis based on the IPCW approach (described in Section 9.7.8) will be performed by integrating data from the prospective and historical cohorts. Similar to the analysis for the Primary Objective, this will be used to provide an estimate of the cumulative incidence rate and number of events in participants receiving DAA therapy when compared to the estimated rates of those participants if they had not received DAA therapy.

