4.5. Population

Prospective Cohort

The prospective DAA-PASS cohort will include a subset of HCV RNA positive participants in the TARGET-HCC study who meet entry criteria including hepatitis C (with no prior history of DAA therapy) and newly diagnosed Barcelona Clinic Liver Cancer (BCLC) Stage A HCC. Participants will be enrolled in the countries participating in TARGET-HCC which will include the United States (US), France, Germany, Italy, and Spain.

Historical Cohort

The historical cohort will be derived from the ITA.LI.CA database, which includes data on all consecutive patients with HCC who were managed within participating centers in Italy. The historical cohort will include patients from the ITA.LI.CA database who have active HCV infection who were not treated for HCV (IFN-based or DAA-based regimens) during the follow-up period, with initial HCC diagnosis BCLC Stage A, and subsequent successful treatment of HCC with curative therapy.

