9.7.3. DAA Exposure as Time-Varying Exposure

Individual participants in the prospective DAA-PASS cohort can contribute person-time to both DAA exposure and no DAA exposure. DAA exposure is a function of time. The no DAA exposure starts at the enrollment/baseline image (Index Date; i.e., successful treatment of HCC) and continues until the participant has an event (i.e., HCC recurrence), initiates DAA therapy, completes the study without initiating DAA therapy, or is otherwise censored. The DAA exposure starts at the first date a DAA is initiated and continues until the participant has an event, completes the study, or is otherwise censored. Participants are censored in whichever exposure type they are in (no DAA exposure or DAA exposure) if they receive IFN treatment, a liver transplant, die, withdraw from the study, or are otherwise removed or lost to follow-up while enrolled in DAA-PASS. Participants that receive DAA therapy starting on the date of Enrollment/Baseline only contribute person-time to DAA exposure and participants that never receive DAA therapy only contribute person-time to the no DAA therapy exposure person-time. The completion of the study is defined by obtaining imaging corresponding to the 24-month follow-up assessment. Note that participants who received a liver transplant while enrolled in DAA-PASS will continue to be followed up to 24 months from Enrollment/Baseline.

Additional information on DAA therapy will be collected including, as available, the DAA prescribed, duration of dosing and planned duration, and SVR response. These will be summarized descriptively.

9.7.4. Coding Convention for HCC Recurrence and DAA as Time-Varying Exposure for the Primary Analysis

This section provides additional details on the coding of the HCC recurrence endpoint for analysis. The primary model of time of onset is based on interval-censoring as outlined in Section 9.7.6.1. The intervals between imaging evaluations are not required to have a fixed length and a participant with a missed visit would simply experience an extended interval -- assuming they have a later follow-up assessment. For the analysis, individuals will have a record of an event or not corresponding to each available interval of no DAA exposure or DAA exposure. The table below provides some examples of participant data where t_{i0} is baseline and t_{ij} for $j = 1$ to n_i represent sequential imaging assessment times for the i^{th} participant:

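### The historical comparator drops ITA.LI.CA patients who later received a DAA instead of censoring them at DAA start, which selects on post-index treatment and can bias Secondary Objectives B and C in an unknown direction

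*Protocol*

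**What the plan says.** Section 9.7.9 builds the historical cohort from ITA.LI.CA and gives the exclusion window in two forms. One is "not treated with DAAs for their HCV infection after HCC diagnosis", which section 4.8 repeats in substance. The other is "who were not treated for HCV (IFN-based or DAA-based regimens) during the follow-up period", which is also the wording of section 4.5; section 7.3 likewise describes these patients as untreated during follow-up. Patients who did receive a DAA are removed whole: "A small number of recently-enrolled patients were treated with DAAs; these patients will be excluded from the historical cohort". How many they are, and whether the DAA came before or after recurrence, is not stated. After these criteria, "there will be approximately 400 eligible patients for inclusion in the historical cohort".

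The prospective cohort follows a different rule. Under section 9.7.3, unexposed time starts at the first HCC-free image and runs to recurrence, DAA start, study completion or censoring. For IFN, "Participants are censored in whichever exposure type they are in (no DAA exposure or DAA exposure) if they receive IFN treatment". Section 9.7.9 confirms that a prospective participant who starts a DAA contributes time to both conditions, while historical patients contribute unexposed time only. It also says that the Secondary Objective B analysis mirrors the primary one.

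**The concern.** Eligibility at time zero is decided by what happened afterwards. A historical patient who was recurrence-free for a year and then received a DAA loses that whole unexposed year. A prospective participant with the same history keeps it. One model thus applies two rules to its unexposed person-time.

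The sign depends on when the DAA was given:

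- **While recurrence-free.** Exclusion removes event-free unexposed time, raises the comparator's recurrence hazard and pulls the pooled hazard ratio below its true value. In a safety study, that direction can hide harm.
- **After recurrence.** Exclusion removes unexposed events and pushes the hazard ratio up.

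The pooled analysis carries real weight. Sections 4.8 and 9.5.1 give no finite upper bound for the primary hazard ratio at 50 prospective participants, and 30 had been enrolled after two years. The exploratory cumulative risk rests on this cohort alone. Section 9.9.2 lists the limitations of the historical comparison without naming this one.

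**Working it through.** **1. The plan's own figure.** Inputs from section 9.7.9: "Based on a convenience sample size of 50 participants in the prospective cohort", about 400 historical patients, true HR 1.0. DAA uptake is from section 9.5.1 (42% by 6 months, a further 44% by 12, 4% more by 24) and follow-up is 24 months. A simulated Cox model with time-varying DAA (1,500 replicates, exponential recurrence, no other censoring) gives:

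| Annual recurrence | Stated 95% CI | Simulated mean 95% CI |
|---|---|---|
| 15% | 0.51-2.13 | 0.52-2.05 |
| 25% | 0.57-1.82 | 0.57-1.76 |
| 35% | 0.62-1.69 | 0.62-1.67 |

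The bounds agree within about 4%. The stated precision is not in dispute.

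**2. Effect on the historical hazard, by hand (25% annual recurrence).** Assumptions: DAA start uniform over 0-24 months and unrelated to recurrence risk, no other censoring.

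- Hazard h = -ln(0.75) = 0.2877 per year.
- Per patient over 2 years: events 1 - 0.75² = 0.4375; person-time 0.4375/0.2877 = 1.5208 years.
- A patient who starts a DAA while recurrence-free has on average 0.9046 years before it and 0.9046 at-risk years after it, with 0.9046 × 0.2877 = 0.2602 events, all after DAA start.
- Drop 10% of the pool: events 0.4375 - 0.1 × 0.2602 = 0.4115; person-time 1.5208 - 0.1 × 1.8092 = 1.3399; hazard 0.4115/1.3399 = 0.3071, or 1.067 times the truth.
- 24-month risk reads 0.4115/0.9 = 45.7% instead of 43.8%; 12-month risk reads 26.9% instead of 25.0%.
- Drop 5%: hazard 0.2968, ratio 1.03.

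If the dropped patients received the DAA after recurrence, each removes one event and on average 0.9046 years. At 5% dropped: (0.4375 - 0.05)/(1.5208 - 0.05 × 0.9046) = 0.3875/1.4756 = 0.2626, or 0.913 times the truth.

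**3. Effect on the pooled hazard ratio.** This is the step 1 model at large size with the same 50:400 proportions, true HR 1.0. It is unadjusted and uses exact event times. The ratio is close to, but not exactly, the reciprocal of the historical distortion, because the unexposed side also holds prospective pre-DAA time and the distortion varies over follow-up.

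| Share of pool dropped (per 400 kept) | Annual recurrence | DAA while recurrence-free | DAA after recurrence |
|---|---|---|---|
| 5% (21) | 15% | 0.973 | 1.187 |
| 5% (21) | 25% | 0.977 | 1.103 |
| 5% (21) | 35% | 0.974 | 1.066 |
| 10% (44) | 15% | 0.956 | 1.474 |
| 10% (44) | 25% | 0.955 | 1.231 |
| 10% (44) | 35% | 0.942 | 1.139 |

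Censoring at DAA start gives 0.99-1.01 in every one of these scenarios.

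**4. Against the stated interval.** At 35% recurrence and 5% dropped, 0.62-1.69 becomes about 0.60-1.65 (× 0.974) or 0.66-1.80 (× 1.066). At 15% recurrence, 0.51-2.13 becomes about 0.50-2.07 (× 0.973) or 0.61-2.53 (× 1.187).

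**The case against.** **Size.** The protocol speaks of "A small number of recently-enrolled patients were treated with DAAs", in a database of diagnoses after 2007 last verified in December 2016. Few patients can have had a DAA within the window. Suppose entry is uniform over nine years and DAAs are available only in the last two or three. With DAA start rates of 5-20% per year, the share dropped is then 1-8% and the hazard ratio is multiplied by 0.94-0.99 when DAAs went to recurrence-free patients. These inputs are also assumed, but they fit the wording better than a large dropped share. This objection stands. A reader might take a loss of a fifth or more of the pool as plausible; the text does not support it.

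**Direction.** A reader might infer that the exclusion makes DAAs look safer. The document does not say when these patients were treated, and step 3 shows the opposite sign if treatment followed recurrence. Section 9.7.9 says that later data were abstracted at recurrence, so DAA use might be recorded more often in patients who recurred, but that is inference.

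**IFN.** The rule also excludes on IFN, where section 9.7.3 censors. Section 9.7.9 reports that ITA.LI.CA patients were not given IFN after successful HCC treatment, so this mismatch should remove almost nobody.

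**Legitimate exclusions.** The longer window also covers DAA use before the first HCC-free image. Those patients are rightly out, as in section 9.2.3.1.

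**Feasibility.** Excluding needs only a yes/no flag; censoring needs a date. The variables listed in section 9.7.9 do not include a DAA start date. However, applying an exclusion confined to follow-up already requires some knowledge of timing.

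**Censoring is not a cure-all.** Its near-perfect result in step 3 follows from making DAA start unrelated to recurrence risk. If DAAs went to selected patients, censoring is informative too.

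None of this justifies the different rules for the two cohorts.

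**Conclusion.** The point holds as a design inconsistency with a modest bias of unknown sign. The historical comparator is selected on post-index treatment while the prospective cohort is not, and the document does not acknowledge it.

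If DAAs were started while recurrence-free, the pooled hazard ratio falls by about 2-3% at 5% dropped and 4-6% at 10%, minor beside an interval of 0.62-1.69 at its narrowest. If they were given after recurrence, it rises to about 1.07-1.19 at 5% dropped, which is less easily ignored. These sizes rest on assumed dropped shares, exponential recurrence and DAA start unrelated to prognosis.

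The affected analyses are Secondary Objectives B and C and the Exploratory Objective. A reader might infer that the study's main result is compromised. It is not: the Primary Objective and Secondary Objective A use the prospective cohort only. This is a should-fix, not a must-fix.

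**What to change.** In sections 4.5, 4.8, 7.3 and 9.7.9:

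- Include every otherwise eligible ITA.LI.CA patient who is DAA-naive at the first HCC-free image. Continue to exclude those given a DAA before it.
- Count unexposed person-time from that image to the first DAA or IFN start and censor there, in line with 9.7.3. Do not switch these patients to exposed: Secondary Endpoints B and C (section 8) take DAA exposure from the prospective cohort only.
- Replace the two exclusion windows with one.
- Report how many patients are affected and when the DAA started relative to recurrence.
- Keep the never-treated set as a sensitivity analysis.
- Apply the model covariates or the inverse-probability-of-censoring weights of section 9.7.8 to this censoring, since it may be informative.

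The cost is one changed extraction rule plus DAA (or IFN) start dates for a small number of patients. The document does not confirm that these dates are held. If they cannot be obtained, the number excluded should still be reported, and the selection and its unknown direction added to section 9.9.2.
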